#### Hepatic Safety Data Collection

Additional safety data should be collected via the hepatic eCRF packet if 1 or more of the following conditions occur:

- elevation of serum ALT to  $\geq$ 5 times ULN on 2 or more consecutive blood tests
- elevated serum TBL to  $\geq 2$  times ULN (except for cases of known Gilbert's syndrome)
- elevation of serum ALP to  $\geq 2$  times ULN on 2 or more consecutive blood tests
- participant discontinued from treatment due to a hepatic event or abnormality of liver tests, or
- hepatic event considered to be an SAE.

# 8.3. Adverse Events and Serious Adverse Events

Adverse events will be reported by the study participant or, when appropriate, by a caregiver, surrogate, or the participant's legally authorized representative.

The investigator and qualified designees are responsible for detecting, documenting, and recording events that meet the definition of an AE (Appendix 10.3, Section 10.3.1) or SAE (Appendix 10.3, Section 10.3.2) and remain responsible for follow-up of AEs through an appropriate health care option (Section 8.3.3).

As noted in Section 8.1, pruritus, angioedema, and hives are monitored as clinical endpoints and would not constitute AEs. However, if any of these events is an SAE as defined in Appendix 10.3, Section 10.3.2, the event should be reported as an SAE. See Section 8.3.6 for more information.

Pregnancy after maternal or paternal exposure to IP does not meet the definition of an AE. However, to fulfill regulatory requirements, any pregnancy should be reported using the SAE process described in Appendix 10.3, Section 10.3.4, to collect data on the outcome for both mother and fetus. See also Section 8.3.5.

# 8.3.1. Time Period and Frequency for Collecting AE and SAE Information

All AEs occurring after signing the ICF are recorded in the eCRF and assessed for serious criteria.

The SAE reporting to the sponsor begins after the participant has signed the ICF and has received IP. However, if an SAE occurs after signing the ICF, but prior to receiving IP, the SAE should be reported to the sponsor as per SAE reporting requirements and timelines (see Appendix 10.3, Section 10.3.3 and Section 10.3.4) if the SAE is considered reasonably possibly related to study procedure.

All SAEs will be recorded and reported to the sponsor or designee immediately upon investigator awareness of the event; under no circumstance should this exceed 24 hours from the time of awareness, as indicated in Appendix 10.3. The investigator will likewise submit any updated SAE data to the sponsor within 24 hours of its availability.

Investigators are not obligated to actively seek AEs or SAEs in study participants once the participants have discontinued and/or completed the study (the Participant Study Disposition eCRF has been completed). However, if the investigator learns of any SAE, including a death, at any time after a participant has been discharged from the study, and the investigator considers the event reasonably possibly related to the study treatment or study participation, the investigator must promptly notify the sponsor.

# 8.3.2. Method of Detecting AEs and SAEs

The method of recording, evaluating, and assessing causality of AEs and SAEs and the procedures for completing and transmitting SAE reports are provided in Appendix 10.3, Section 10.3.3 and Section 10.3.4.

Care will be taken not to introduce bias when detecting AEs and/or SAEs. Open-ended and nonleading verbal questioning of the participant is the preferred method to inquire about AE occurrences.

# 8.3.3. Follow-Up of AEs and SAEs

After the initial AE or SAE report, the investigator is required to proactively follow each event at subsequent visits and/or contacts with the participant.

All SAEs and AEs that are otherwise medically important, or that are considered related to the IP or study procedures, or that caused the participant to discontinue the IP before completing the study, will be followed up until the event is resolved, stabilized, or otherwise explained, or until the participant is lost to follow-up (as defined in Section 7.3). The frequency of follow-up evaluations is at the discretion of the investigator.

Further information on follow-up procedures is provided in Appendix 10.3, Section 10.3.3.

#### 8.3.4. Regulatory Reporting Requirements for SAEs

Prompt notification by the investigator to the sponsor of an SAE, as stated in Section 8.3.1, is essential so that legal obligations and ethical responsibilities toward the safety of participants and the safety of a study intervention under clinical investigation are met.

The sponsor has a legal responsibility to notify both the local regulatory authority and other regulatory agencies about the safety of a study intervention under clinical investigation. The sponsor will comply with country-specific regulatory requirements related to safety reporting to the regulatory authority, Institutional Review Boards (IRBs)/Independent Ethics Committees (IECs), and investigators.

Investigator safety reports must be prepared for suspected unexpected serious adverse reactions (SUSARs) according to local regulatory requirements and sponsor policy and forwarded to investigators as necessary.

An investigator who receives an investigator safety report describing an SAE or other specific safety information (for example, summary or listing of SAEs) from the sponsor will review and then file it along with the IB and will notify the IRB/IEC, if appropriate according to local requirements.

#### 8.3.5. Pregnancy

For all pregnancies in female participants and female partners of male participants, details will be collected for pregnancies that begin at any point after the start of study drug and until at least 12 weeks after the participant's last dose of study drug.

If a pregnancy is reported, the investigator should inform the sponsor within 24 hours of learning of the pregnancy and should follow the procedures outlined in Appendix 10.3, Section 10.3.3 and Section 10.3.4; and Appendix 10.4.

Abnormal pregnancy outcomes (for example, spontaneous abortion, fetal death, stillbirth, congenital anomalies, ectopic pregnancy) are considered SAEs.

# 8.3.6. Study Endpoints Not Qualifying as Adverse Events

The following events are being captured as study endpoints and will not be reported as AEs:

- Pruritus (itching)
- Angioedema
- Hives (wheals)

Information on these events will be captured via the UPDD (patient electronic diary).

However, if any of these events is an SAE as defined in Appendix 10.3, Section 10.3.2, the event should be reported as an SAE.

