#### Urticaria Patient Daily Diary (UPDD)

The UPDD is a daily diary completed twice per day (morning and evening) via an electronic, handheld device. Items asking about itch severity and number of hives pertain to the past 12 hours and are asked twice per day. The remaining items are asked once per day and pertain to the past 24 hours: interference with sleep, interference with daily activities, use of rescue medication (number of tablets), presence (and treatment) of angioedema, and any calls placed to healthcare professionals. While developed originally on paper, the electronic version of the UPDD has been shown to be equivalent to the paper version from a measurement perspective, and is considered a valid and reliable assessment of urticaria symptoms (Flood et al. 2013).

Pruritus, angioedema, and hives are monitored as clinical endpoints in the UPDD and would not constitute AEs. However, if any of these events is an SAE as defined in Appendix 10.3, Section 10.3.2, the event should be reported as an SAE. See Section 8.3.6 for more information.

There is no overall UPDD score calculation. The primary endpoint assessment (Urticaria Activity Score Over 7 Days [UAS7]) and key secondary endpoint assessments (Itch Severity Score Over 7 Days [ISS7] and Hives Severity Score Over 7 Days [HSS7]) are derived from data collected via the UPDD, as described below (Sections 8.1.1 and 8.1.2, respectively).

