#### 8.3.7.1. Infusion Reactions

Symptoms of a local infusion site reaction may include erythema, induration, pain, and edema. Worsening of CSU symptoms present at baseline does not necessarily constitute an infusion reaction, per the investigator's determination (see Section 8.3.6). If an infusion site event is reported, the AE will be recorded, and additional data will be provided to the sponsor in the eCRF.

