### 10.3.3. Recording and Follow-Up of AE and/or SAE

### AE and SAE Recording

When an AE/SAE occurs, it is the responsibility of the investigator to review all documentation (for example, hospital progress notes, laboratory reports, and diagnostics reports) related to the event.

The investigator will then record all relevant AE/SAE information in the CRF.

It is **not** acceptable for the investigator to send photocopies of the participant's medical records in lieu of completion of the AE/SAE CRF page.

There may be instances when copies of medical records for certain cases are requested. In this case, all participant identifiers, with the exception of the participant number, will be redacted on the copies of the medical records before submission.

The investigator will attempt to establish a diagnosis of the event based on signs, symptoms, and other clinical information. Whenever possible, the diagnosis (not the individual signs/symptoms) will be documented as the AE/SAE.

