3.3. Exploratory Objectives

Exploratory objectives and endpoints may include the following:

Objectives/Endpoints

- To evaluate signs and symptoms and measures of quality of life at various time points in Period 2 (first 12 week treatment period) and in Period 3 (second 12-week treatment period, after crossover) using the DLQI and the UPDD items.
- To assess the potential development of anti-LY3454738 antibodies and their impact on the safety profile and PK of LY3454738.
- To explore relationships between LY3454738 exposure and select biomarkers and clinical efficacy endpoints.

4. Study Design

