5.3.2. Definition of Baseline and Postbaseline Measures

The baseline value for Period 2 is defined as the last nonmissing measurement on or before the date of first study drug administration (expected at Week 0). The baseline value for Period 3 is the last available value before the initial dose in Period 3 (expected at Week 12). Other definitions of the baseline value may be used to conduct additional supporting analyses.

A number of efficacy outcome measures are in the form of weekly scores derived from patient daily diary data. For these measures, the weekly score will be derived from the 7 days immediately prior to the study visit. The baseline score will be derived from the 7 days prior to Day 1 (Visit 2) for Period 2, and 7 days prior to Day 85 (Visit 9) for Period 3.

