5.7.6. Special Safety Topics, including Adverse Events of Special Interest

In addition to general safety parameters, safety information on specific topics of special interest will also be presented. Additional special safety topics may be added as warranted. The topics outlined in this section include the protocol-specified AESI.

In general, for topics regarding safety in special groups and circumstances, patient profiles and/or patient listings, where applicable, will be provided when needed to allow medical review of the time course of cases/events, related parameters, patient demographics, study drug treatment and meaningful concomitant medication use. In addition to the safety topics for which provision or review of patient data is specified, these will be provided when summary data are insufficient to permit adequate understanding of the safety topic.

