5.7.6.4. Allergic Reactions/Hypersensitivities

A search will be performed using the current MedDRA version 20.0 SMQs to search for relevant events, using the following queries:

- Anaphylactic reaction SMQ (2000021)
- Hypersensitivity SMQ (20000214)
- Angioedema SMQ (2000024)

Events that satisfy the queries will be listed, by temporal order within patient ID, and will include SOC, PT, SMQ event categorization including detail on the scope (narrow or broad), reported AE term, AE onset and end dates, severity, seriousness, outcome, etc.

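### Non-serious angioedema is kept out of AE reporting because the diary captures it, yet no analysis in the SAP tables uses the diary's angioedema item

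*Protocol*

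**What the plan says.** Protocol Section 8.3.6 lists pruritus, angioedema and hives and says: "The following events are being captured as study endpoints and will not be reported as AEs". The diary (UPDD) is to hold this information, and the one exception is an event that qualifies as an SAE. SAP Section 5.7.2 repeats the list and the exception.

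The diary description in Protocol Section 8.1 includes, among the once-daily items with 24-hour recall, "presence (and treatment) of angioedema". An exploratory objective in SAP Section 3.3 concerns signs, symptoms and quality of life "using the DLQI and the UPDD items", under an introduction saying only that such objectives may be included.

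For allergic reactions, SAP Section 5.7.6.4 plans MedDRA query searches, one of them for angioedema: "Events that satisfy the queries will be listed, by temporal order within patient ID".

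Several provisions keep some reactions reportable. Section 10.3.3 says: "Whenever possible, the diagnosis (not the individual signs/symptoms) will be documented as the AE/SAE". Section 8.3.7 makes anaphylaxis and infusion reactions AEs of special interest. Section 8.3.7.1 adds that worsening of CSU symptoms present at baseline "does not necessarily constitute an infusion reaction, per the investigator's determination", and refers back to 8.3.6.

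**The concern.** Keeping symptoms of the disease under study out of AE reporting is a reasonable choice when they are analysed elsewhere. Here the stated reason is that they are captured as study endpoints. For angioedema the capture takes place, but no listed analysis uses it.

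This matters because the symptoms left out are also ways in which a reaction to an infused antibody can show itself. Section 8.3.7.2 says that all biologic agents carry a risk of systemic hypersensitivity, and Section 2.2 says this is the first study of the antibody in CSU. Participants enter with UAS7 of 16 or more, so a mild reaction is hard to tell from the disease in a single patient. A comparison of the arms around infusions could show an excess that case-by-case judgement would miss. The daily diary entries and the recorded dose times would support it, but no planned analysis uses them in this way.

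**Working it through.** **1. Check of the day numbers.** The Schedule of Activities puts the last dose on day 155 and the follow-up visits on days 197 and 239. (197 − 155)/7 = 6 weeks and (239 − 155)/7 = 12 weeks, which agrees with Protocol Section 4.1.

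**2. Where can non-serious angioedema appear, if it is not diagnosed as part of a reaction?**

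| Place in the plan | Does it enter? |
|---|---|
| AE tables, SAP 5.7.2 | No, excluded by rule |
| Query listings, SAP 5.7.6.4 | No. They show the reported AE term, onset and severity, so they draw on recorded events |
| UAS7, ISS7, HSS7, Protocol 8.1.1 and 8.1.2 | No. They are built from itch and hives only |
| SAP Tables FRCF.5.1, 5.2 and 5.3 (Period 3 efficacy) | No. The measures are UAS7, ISS7, HSS7 and DLQI |
| Exploratory objective, SAP 3.3 | The UPDD items are named, but no table row takes up angioedema |
| Safety trigger, Protocol 10.1.9 | No. It counts TEAEs |

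SAP Section 5.7.6 also has no subsection on infusion reactions, although the protocol names them as of special interest.

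**3. Section 8.3.6 beside Section 10.3.1.** Take severe but non-serious angioedema that is clearly worse than the participant's usual disease.
- Under 10.3.1 it is an AE. Signs of the disease under study are exempt only if they are no worse than expected for that participant, and an increase in the frequency or intensity of a pre-existing condition counts as an AE.
- Under 8.3.6 it is not reported, because seriousness is the only exception.
- The trigger in 10.1.9 needs three or more participants with TEAEs in one system organ class that are severe and/or serious and judged related. A site that follows 8.3.6 contributes nothing to that count.

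Section 7.1.1 has a criterion of its own for stopping study drug, namely whether the reaction differs from the CSU symptoms at baseline. Section 8.3.6 has no criterion.

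**4. Can the weekly scores stand in for itch and hives?** SAP Section 5.3.2 says: "For these measures, the weekly score will be derived from the 7 days immediately prior to the study visit". A visit on day d therefore scores days d − 7 to d − 1.
- Period 2 visits on days 8, 15, 29, 43, 57, 71 and 85 score 7 × 7 = 49 of 84 days.
- The infusions are on days 1, 15, 29, 43, 57 and 71. The 84 − 49 = 35 unscored days are the 5 × 7 days that begin with infusions 2 to 6. Period 3 repeats the pattern.
- With ±3 days at both visits, the gap g from one of these infusions to the next visit is 8 to 20 days, and days g − 7 to g − 1 after the dose are scored. At g = 8, 6 of the first 7 days (days 0 to 6) are scored; at g = 14 or more, none. The infusion day itself is never scored.

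This shows only that the efficacy scores cannot replace an analysis around infusions. Full scoring would not change that: a one-day rise of 1 point in the daily hives score moves HSS7, which runs from 0 to 21, by 1 point.

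**5. What a diary table would have to work with.** Randomizing 60 participants 3:1 gives 60 × 3/4 = 45 on LY3454738 and 60 × 1/4 = 15 on placebo in Period 2. The last Period 2 dose is on day 71 and the first Period 3 dose on day 85. The interval of 14 days is about one half-life (about 2 weeks, Protocol Section 4.2), so about half the drug level remains when Sequence Group 1 starts placebo. Period 2 is the clean comparison.

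**The case against.** The strongest reply is that little is left after the routes that stay open.
- Reactions diagnosed as anaphylaxis, hypersensitivity or infusion reaction remain reportable, and so do serious cases.
- Section 8.3.7.2 provides for extra samples in generalized urticaria, so hives as a drug reaction are foreseen.
- Participants are watched for at least 30 minutes after dosing. Skin is examined and AEs are asked about at every visit.
- The remark in 8.3.7.1 covers only symptoms present at baseline, so new angioedema does not fall under it.

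All of this stands, and it narrows the gap to non-serious episodes that nobody diagnoses as a reaction.

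A second reply is that nothing is lost. The diary is kept daily, Protocol Section 9.4 allows further exploratory analyses, and SAP Section 5.7.6 says: "Additional special safety topics may be added as warranted". It is true that the data will exist. But the permission does not commit anyone to the analysis, and the AE data that would normally prompt it are the data from which these symptoms are excluded.

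A third reply is that the sentence proposed for 8.3.6 largely repeats 10.3.1. That is partly right. It harmonises the text, and it is needed because 8.3.6 reads as a flat exclusion.

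A reader might infer from the weekly windows that reactions to five of six infusions go unseen. The documents do not support this. The windows belong to efficacy scores, which would not isolate a brief reaction in any case, and they say nothing about how many reactions are missed.

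**Conclusion.** The point holds in a limited form. Followed as written, the plan puts non-serious angioedema that is not diagnosed as part of a reportable reaction into no planned safety or efficacy summary, and it plans no look at itch, hives or angioedema around infusions. Sections 8.3.6 and 10.3.1 give sites conflicting instructions, so a severe non-serious case can be left out of the AE tables and the 10.1.9 count.

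The number of affected episodes cannot be estimated, because the documents give no rate of angioedema or of mild reactions. A reader might infer that hypersensitivity in general goes unreported, or that the information is lost. Neither follows: diagnosed and serious reactions are reported, itch and hives do enter the weekly scores, and the gap is in the planned analysis, not in the collection of data.

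The conclusion assumes that the SAP's Period 2 and Period 3 efficacy analysis tables are complete as published and that sites apply 8.3.6 literally. It is a cheap improvement, minor to moderate in weight, and it does not touch the primary efficacy result.

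**What to change.** 1. In SAP Section 5.7.6.4, add a descriptive diary table by arm, with Period 2 as the main comparison and Period 3 shown descriptively because there is no washout. Give the number of participants and of days with angioedema, and the daily itch and hives scores, on the infusion day and the next day against the 3 days before that infusion. For itch and hives on the infusion day use the evening entry, because Section 8.1 has self-assessments completed before visit procedures. State in a footnote that the 12-hour recall (itch, hives) and the 24-hour recall (angioedema) may still mix time before and after the dose.

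2. In Protocol Section 8.3.6 and SAP Section 5.7.2, add one sentence: hives, itch or angioedema are reported as AEs when the investigator judges them worse than expected for that participant (the 10.3.1 test) or unlike the participant's CSU symptoms at baseline (the 7.1.1 test). Say that the second test is borrowed for AE reporting only and leaves the stopping criterion in 7.1.1 as it is. Such events then count toward the 10.1.9 trigger when its other conditions are met. The carve-out for ordinary disease symptoms stays.

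The cost is one table from data already collected, one sentence in two documents, and some extra AE entries. With about 15 placebo participants in Period 2 precision will be low, so the table should carry no formal test.

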# 8.3.7. Adverse Events of Special Interest

Adverse events of special interest for this study include anaphylaxis, infusion reactions, and infections. If such AEs are reported, sites will be prompted to collect additional data as described in the following subsections.

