#### 8.3.7.2. Allergic Reactions and Hypersensitivity Events

All biologic agents carry the risk of systemic allergic/hypersensitivity reactions. Clinical manifestations of these reactions may include but are not limited to:

- skin rash
- dyspnea
- hypotension, and
- anaphylactic reaction (Sampson et al. 2006).

Participants with clinical manifestations of systemic allergic/hypersensitivity reactions should be treated per local standard of care. Additional data describing each symptom should be provided to the sponsor in the eCRF.

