4.1. Summary of Study Design

Study J1B-MC-FRCF (FRCF) is a multicenter, randomized, double-blind, placebo-controlled, Phase 2 crossover study to evaluate the efficacy and safety of LY3454738 500 mg given intravenously (IV) every 2 weeks (Q2W) versus placebo IV Q2W in adults with CSU inadequately controlled with H₁-antihistamines.

The study duration will be up to approximately 39 weeks over 4 study periods, as shown below:

Period 1: Screening, lasting up to 35 days before Week 0 (Visit 2, baseline)

Period 2: First 12-week treatment, from Week 0 (Day 1) through Week 12:

• Participants will be randomized in a 3:1 ratio to receive either LY3454738 500 mg IV or placebo IV Q2W

Period 3: Second 12-week treatment (crossover), from Week 12 through Week 24:

- Participants who received LY3454738 500 mg IV in Period 2 will receive placebo IV Q2W in Period 3.
- Participants who received placebo IV in Period 2 will receive LY3454738 500 mg IV Q2W in Period 3.

Period 4: Post-treatment follow-up for approximately 10 weeks.

- Participants will not receive study drug in Period 4.
- The last dose of study drug is given at Week 22, which is 6 weeks before the first post-treatment follow-up visit (Visit 801). Thus, participants will have been withdrawn from study drug for a total of 12 weeks at the last post-treatment follow-up visit (Visit 802).

Approximately 85 patients will be screened to achieve approximately 60 randomized participants. A total of approximately 52 evaluable participants are expected.

Throughout the study, participants will take a second-generation H_1 -antihistamine at a dose specified in approved product labeling. Certain participants may receive rescue therapy as described in Section 6.5.2 in the protocol.

Participants who permanently discontinue the study drug early will undergo early termination procedures, including an early termination visit (ETV) and the post-treatment follow-up visits specified in the Schedule of Activities (SoA) (Section 1.3 in the protocol).

Figure FRCF.4.1 illustrates the study design. The blinding procedure is described in the Protocol.

[figure not shown]

Figure FRCF.4.1. Illustration of study design for Clinical Protocol J1B-MC-FRCF.

Abbreviations: C = crossover visit; D = day; Q2W = every 2 weeks; R = randomization visit; W = study week relative to randomization visit; V = visit.

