The frequency and percentages of patients with TEAEs will be summarized by treatment using MedDRA PT nested within SOC. Events will be ordered by decreasing frequency within SOC. The frequency and percentages of patients with TEAEs by maximum severity will also be summarized by treatment using MedDRA PT nested within SOC.

Fisher's exact test will be performed to compare percentages for each LY3454738 dose group and Placebo at both the SOC and PT levels.

Listings will be presented for all AEs, all SAEs, all AEs leading to death, all AEs leading to study drug temporary interruption, and all AEs leading to discontinuation from the study.

In this study, the following events are being captured as study endpoints and will not be reported as AEs:

- Pruritus (itching)
- Angioedema
- Hives (wheals)

Information on these events will be captured via the UPDD (patient electronic diary).

However, if any of these events is an SAE, the event should be reported as an SAE.

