5.7.6.3. Infections

Infections will be defined using the PTs from the MedDRA Infections and Infestations SOC, with additional terms from the Investigations SOC being used in selected instances, as described below.

Treatment-emergent infections will be analyzed according to various groups of infectious events including:

- all infections
 - o all PTs in the Infections and Infestations SOC,
- serious infections
 - o all PTs in the Infections and Infestations SOC that are SAEs,
- infections that require therapeutic intervention (antibiotics, antivirals, antifungals, and so on)
 - all PTs in the Infections and Infestations SOC for which there is an antimicrobial concomitant medication associated with that event for that subject,
- herpes zoster
 - specific Lilly-defined PTs from the Herpes Viral Infections high-level term (HLT) in the Infections and Infestations SOC, shown in Appendix 1,
- tuberculosis
 - specific Lilly-defined PTs from the Tuberculous Infections HLT and the Investigations SOC, shown in Appendix 2
- viral hepatitis
 - all PTs from the Hepatitis Viral Infections HLT (HLT code 10057212) in the Infections and Infestations SOC.

J1B-MC-FRCF (c) Statistical Analysis Plan Version 2

For each infection event, the frequency for each PT will be provided, ordered by decreasing frequency in the LY3454738 highest dose group by infection group: all infections, serious infections (overall and on each approach to identifying SAEs), infections that require therapeutic intervention, herpes zoster infections, tuberculosis, and viral hepatitis.

In addition to the incidence of infectious AEs by MedDRA PT as described above, the number and percentage of subjects with treatment-emergent infectious AEs by treatment group will be summarized and listed.

Potential Opportunistic Infections:

Potential opportunistic infections (POIs) will be identified according to 2 different approaches.

POIs are identified from TEAEs based on a Lilly-defined list of MedDRA PTs, shown in the Appendix 3. These PTs are a subset of terms from the Infections and Infestations SOC.

For the POIs identified from MedDRA PTs, the number and percentage of subjects overall and for each specific PT will be summarized by treatment group, with specific event terms ordered by decreasing frequency in the LY3454738 highest dose.

Association of Infections with Lymphopenia or Neutropenia:

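### The SAP only lists the anaphylaxis and hypersensitivity SMQ hits, so no planned table gives the number of participants with at least one such event by treatment, and an excess spread across SOCs is pooled nowhere.

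*Protocol*

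**What the plan says.** **What is singled out.** Protocol 8.3.7: "Adverse events of special interest for this study include anaphylaxis, infusion reactions, and infections". Protocol 8.3.7.2, placed under the same AESI heading: "All biologic agents carry the risk of systemic allergic/hypersensitivity reactions". It names skin rash, dyspnea, hypotension and anaphylactic reaction as possible manifestations.

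**What the SAP does with it.** SAP 5.7.6.4 runs three SMQs: anaphylactic reaction, hypersensitivity and angioedema. The stated output is: "Events that satisfy the queries will be listed, by temporal order within patient ID". The named fields include SOC, preferred term, SMQ scope, onset and end dates, severity, seriousness and outcome. The list is open-ended. Treatment at onset and time since the last infusion are not among the named items.

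**What the neighbouring AESI gets.** SAP 5.7.6.3, on infections: "the number and percentage of subjects with treatment-emergent infectious AEs by treatment group will be summarized and listed".

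**What the general tables give.** SAP 5.7.2: "The frequency and percentages of patients with TEAEs will be summarized by treatment using MedDRA PT nested within SOC", and "Fisher's exact test will be performed to compare percentages for each LY3454738 dose group and Placebo at both the SOC and PT levels". Serious events (5.7.2.1) and events leading to discontinuation of study treatment (5.7.2.2) are also tabulated by treatment.

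**What is not collected as an adverse event.** SAP 5.7.2: "In this study, the following events are being captured as study endpoints and will not be reported as AEs". These are pruritus, angioedema and hives, unless serious.

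**The concern.** An SMQ search exists to bring together terms that MedDRA places in different parts of its hierarchy. Here the search is run, but its result is never turned into a count of participants by treatment. A reader of the study report could not take from any planned table the proportion of participants on LY3454738 and on placebo who had at least one hypersensitivity event. Yet this is a risk the protocol itself names for an intravenous antibody. Preferred-term and SOC rows do not supply the figure. SOC rows also contain unrelated events, and they cannot be added, because one participant may appear in several.

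The crossover makes a listing harder to read. A participant who completes both periods receives both treatments, so events on drug and on placebo sit in the same patient block. Unless treatment at onset is shown, the reader has to work it out from the dates.

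**Working it through.** **1. The plan's own figures.** The documents give no expected hypersensitivity rate and no power for a safety comparison. The only design figure is power of about 87% for UAS7, and this point does not rest on it. It reproduces at 3:1 with 52 evaluable participants (39 versus 13). SE = 7 × √(1/39 + 1/13) = 2.242 and 7/2.242 = 3.122, so power ≈ Φ(3.122 − 1.960) = 87.7%. The noncentral t gives 86.5%.

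**2. Group sizes in Period 2.** SAP 4.1: "Participants will be randomized in a 3:1 ratio to receive either LY3454738 500 mg IV or placebo IV Q2W". With 60 randomised and all assumed dosed, that is 60 × 3/4 = 45 on LY3454738 and 60 × 1/4 = 15 on placebo.

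**3. Where an SMQ hit is counted.**

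| Planned output | By treatment? | Pools terms? | Participants with at least one hypersensitivity event? |
|---|---|---|---|
| Preferred-term rows (SAP 5.7.2) | yes | no | no |
| SOC rows (SAP 5.7.2) | yes | within one SOC, mixed with unrelated events | no |
| SAE and discontinuation tables (SAP 5.7.2.1, 5.7.2.2) | yes | as above, qualifying events only | no |
| SMQ listing (SAP 5.7.6.4) | not stated | yes, but not counted | no |

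**4. Size, on assumed counts.** Suppose 12 LY3454738 participants and no placebo participants each have one hit, over four preferred terms with three participants each. Suppose also that no other events fall in the same SOCs. With no placebo events and k events in total, the observed table has probability C(45,k)/C(60,k). The two-sided Fisher p adds every table that is no more likely.

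- Four terms in four different SOCs: each planned row reads 3/45 versus 0/15. The observed table has probability 0.415, and p = 0.57.
- Pooled by SMQ: 12/45 (26.7%) versus 0/15. The observed table has probability 0.0206, and p = 0.027.
- The same four terms in one SOC: the planned SOC row already reads 12/45 versus 0/15, p = 0.027. Here nothing is hidden.

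**5. What a pooled count can detect.** Against 0/15 on placebo:

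| LY3454738 | p |
|---|---|
| 3/45 | 0.57 |
| 6/45 | 0.32 |
| 9/45 | 0.095 |
| 11/45 | 0.051 |
| 12/45 | 0.027 |

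Exact power of the pooled test, enumerating both binomials, is 13% at assumed true rates of 20% versus 2%, 63% at 30% versus 2%, and 93% at 40% versus 2%. With one fifth of the 30% or 40% rates in each of five terms, the power for any single term is below 0.1%. The exact two-sided 95% upper limit for 0/15 is 1 − 0.025^(1/15) = 21.8%, so placebo alone leaves wide uncertainty.

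**The case against.** The strongest reply is that these events are already counted by treatment. This is largely right.

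- A reader might infer that an excess spread over several preferred terms would be invisible. The SAP does not support that: SOC rows pool preferred terms and are tested. Only an excess spread across SOCs is left unpooled.
- Protocol 10.3.3 asks for the diagnosis rather than its separate signs and symptoms where possible. Anaphylaxis would then be one preferred term with its own row by treatment. It would also appear in the SAE table if serious, and in the discontinuation table if study treatment is stopped because of it. That limits the scattering, mainly for anaphylaxis. It does less for reactions recorded as rash, dyspnea or hypotension without a unifying diagnosis.
- A reader might infer that the listing hides treatment. The field list is open-ended, and the general text of SAP 5.7.6 allows profiles or listings that include study drug treatment when needed. The fair statement is that treatment at onset is not specified.
- A reader might infer that the trial cannot produce a hypersensitivity rate by treatment. It can: hits are identified and dated, and treatment is known. What is missing is a prespecified display.
- Protocol 8.3.7 lists anaphylaxis, not all hypersensitivity, as the AESI. That is so, although 8.3.7.2 sits under the AESI heading and the SAP itself chose the wider searches.
- Non-serious hives, angioedema and pruritus are not reported as adverse events, so any SMQ count is incomplete for those terms. This stands, and the table must say so.

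The absence of a participant-level count by treatment survives all of these.

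**Conclusion.** The gap is real and modest. For a protocol-named AESI and its related stated risk, the SAP stops at a listing, while infections get a pooled count by treatment. No reason is given for the difference. The participant-level hypersensitivity rate by treatment, and any excess spread across SOCs, appear in no planned table.

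The 0.57 versus 0.027 contrast rests on assumed counts, an even split over four SOCs, no other events in those SOCs, and all 60 participants dosed. It shows how the display works and does not predict a result. With 0/15 on placebo, at least 12/45 is needed for p < 0.05. The table's value is therefore mainly descriptive, and a non-significant result would not show that the risk is absent. The change is still worth making, because it gives the one figure a reader would look for and uses searches already planned.

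**What to change.** In SAP 5.7.6.4:

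1. Add a table for each SMQ, narrow and broad scope separately. Give the number and percentage of participants with at least one treatment-emergent event, by treatment actually received in each period.
2. Treat Period 2 as the randomised comparison, with Fisher's exact test or a confidence interval labelled descriptive. Show Period 3 separately.
3. Settle the grouping first. SAP 5.3.1 analyses safety by the intervention received within each period, whereas SAP 5.7 uses the product randomised at Week 0. In Period 3 these put the same participant under opposite treatments. Use the 5.3.1 definition here and reconcile 5.7 with it.
4. Assign events after the Visit 9 infusion to Period 3. SAP 5.7.2 counts Visits 2 to 9 as Period 2, but the protocol's Schedule of Activities has dosing at Visit 9, the crossover visit. A reaction to the first crossover infusion could otherwise be counted in the wrong period.
5. Add treatment at onset and days since the last infusion to the listing.
6. Footnote that non-serious hives, angioedema and pruritus are not reported as adverse events, so the counts exclude them.

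The cost is SAP wording and one more, mainly descriptive, table. No new data or searches are needed. Items 3 and 4 are decisions that the other by-treatment safety tables need as well.
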